Secondary To determine the pharmacokinetics of LY3478045 following single and multiple doses in healthy subjects.	AUC(0-24), AUC(0-inf), C _{max} , and t _{max} .

Abbreviations: AUC(0-24) = area under concentration versus time curve from time zero to 24 hours; AUC(0-inf) = AUC from time zero to infinity; C_{max} = maximum observed drug concentration; SAE = serious adverse event; t_{max} = time of C_{max}; TEAE = treatment-emergent adverse event.

Summary of Study Design:

Study GZKA is a Phase 1, single site, randomized, double-blind, placebo-controlled, 2-part study of LY3478045 in healthy subjects.

Part A: single-ascending dose.

Part B: multiple-ascending dose design that evaluates the potential for a drug-drug interaction.

In Part A, single-ascending oral doses of either LY3478045 or placebo will be administered in up to 5 cohorts. Each cohort will consist of at least 8 subjects, 6 subjects will receive LY3478045 and 2 subjects will receive placebo. Cohort 5 is an optional cohort that may be assessed based on the available safety and PK data from the previous 4 cohorts.

Part B will be initiated after assessing safety, tolerability, PK, and PD data through Cohort 3 in Part A.

Multiple-ascending oral doses of LY3478045 will be administered once daily for 14 days in up to 4 cohorts. Each cohort will consist of at least 8 subjects. In Cohorts 1 and 3, six subjects will receive LY3478045 and 2 subjects will receive placebo. In Cohorts 2 and 4, six subjects will receive LY3478045 followed by a single dose of **CC1** and 2 subjects will receive placebo followed by a single dose of atorvastatin **CC1** later.

Treatment Arms and Planned Duration for an Individual subject:

Treatment Name	LY3478045	Placebo	Atorvastatin
Dosage Formulation	CC1	Capsules	Tablets
Dose strength	CC1	-	40 mg
Route of Administration	Oral	Oral	Oral

The planned duration for each subject is approximately 43 days in Part A and 57 to 59 days in Part B of the study.

Number of Subjects:

Up to 50 subjects may be enrolled in Part A to ensure that at least 40 subjects complete the study (depending on whether subjects will be enrolled in optional Cohort 5). Up to 40 subjects may be enrolled in Part B to ensure that at least 32 subjects complete the study.

Statistical Analysis:

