2.3. Part B (Cohorts 2 and 4; Multiple-Ascending Doses)

Procedure	Screening ≤28 days before Day -3	Days												FU ^a	ED ^b	Comments
		-3	-2	-1	1	2	3 to 6	7	8	9 to 13	14	15, 16, 17				
Informed Consent	X															
Admission to CRU ^c		X														
Discharge from CRU													Day 17			
LY3478045 Administration							X									
Medical History	X														Information regarding occasional use of vitamin/mineral supplements will be taken as a part of the medical history evaluation at the time of subject screening.	
Complete Physical Examination	X													X	X	Targeted PE may be conducted at other visits at the discretion of the investigator.
Height	X															
Weight	X	X											Day 15	X	X	
Pregnancy Test	X	X												X	X	Serum pregnancy test will be performed at screening and urine pregnancy test will be performed at all other specified timepoints.
Blood Pressure and Pulse Rate (Supine) ^c	X			X	P, every 1 h up to 12 h postdose	24, 36 h	48, 72 h						X		X	
Body Temperature	X			X										X	X	
Clinical Laboratory Tests (See Appendix 2)	X	X			P		Day 4	X					X		X	
Total Testosterone, Follicle-Stimulating Hormone, and Luteinizing Hormone	X				P	P								X	X	Samples will be collected early in the morning on Days 1 and 2, at the same time for both days, before or immediately

	Screening	Days											FU ^a	ED ^b	Comments
Procedure	≤28 days before Day -3	-3	-2	-1	1	2	3 to 6	7	8	9 to 13	14	15, 16, 17	28		
															after breakfast.
Serum Creatinine					X			X			X				
Single 12-Lead ECG	X											X	X		
TriPLICATE 12-Lead ECG					Predose: 1.5 h, 1 h, and 30 min.						P, 0.5, 1.5, 2.5, 4, 6, 8, 12, 16 h	24 h			
Adverse Event Recording	X	X	X	X	X	X	X	X	X	X	X	X	X		
Pharmacokinetic Sampling ^d					P, 0.75, 1.5, 3, 4, 6, 8, 12, 16 h	24 h (predose)		P, 0.75, 1.5, 3, 4, 6, 8, 12, 16 h	24 h (predose)		P, 0.75, 1.5, 3, 4, 6, 8, 12, 16 h	24, 48, 72 h		Sampling times may be adjusted based upon review of interim PK	
Fasting insulin and Adiponectin					P						P				
Meal (Low Fructose)			breakfast		20 min, 6, 12 h			20 min			20 min, 6, 12 h				
Fructose Beverage (for Fructose Tolerance Test)					during meal: 20 min, 6, 12 h						during meal: 20 min, 6, 12 h				
Fructose Tolerance Test Assay ^d					CCl	24 h (predose and premeal)					CCl	CCl			
CCl				X				X							Atorvastatin will be administered 4 hours after LY3478045 administration on Day 7 or 4 hours after breakfast on Day -2.

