CCl				P, 0.5, 1, 2, 3, 4, 6, 20, 32 h	48 h			P, 0.5, 1, 2, 3, 4, 20, 32 h	48 h						Sampling times are relative to the time of
Pharmacokinetics															

Procedure	Screening ≤28 days before Day -3	Days											FU ^a	ED ^b	Comments
		-3	-2	-1	1	2	3 to 6	7	8	9 to 13	14	15, 16, 17			
			8, 12 h					6, 8, 12 h							atorvastatin administration
Genetic Sample				P											
Fasting Biomarker Samples (Nonpharmacogenetic)				X		X						Day 15			
CCI			P, 1.5, 3, 4, 6, 8, 12, 16 h	24 h (predose)	P, 1.5, 3, 4, 6, 8, 12, 16 h	24 h (predose)		P, 1.5, 3, 4, 6, 8, 12, 16 h	24 h (predose)						Sampling times may be adjusted based upon review of preliminary data

Abbreviations: CRU = clinical research unit; ECG = electrocardiogram; ED = early discontinuation; FU = follow-up; h = hour(s); min = minutes; P = predose; PE = physical examination; PK = pharmacokinetics.

Notes: if multiple procedures take place at the same time point, the following order of the procedures should be used: ECG, vital signs, and venipuncture. Samples collected for clinical laboratory tests including urine analysis may be analyzed at a local laboratory. All time points specified in the table are approximate and may be adjusted at the discretion of the investigator.

- ^a Additional FU visits may occur depending upon emerging pharmacokinetic and/or safety data.
- ^b At the discretion of the investigator, subjects may be requested to return to the CRU for safety monitoring at additional visits following completion of the ED procedures. At the discretion of the investigator, assessments may include, but will not be limited to, those presented for the FU visit with the addition of safety laboratory tests.
- ^c Where possible, measurements of blood pressure and pulse rate should be performed at approximately the same time of day at each scheduled time point. Time points may be added for each study period, if warranted and agreed upon between Lilly and the investigator.
- ^d Sampling times are relative to the time of study treatment administration (0 min). Time of breakfast represents 0 min on study Day -2.
- ^e If the predicted mean exposure for the dose at any cohort is estimated to be higher than 71.7 µg·hr/mL, only female subjects will be included in the cohort and mandated to stay in the CRU until 24 hours after the last dose.

3. Introduction

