5.5. Justification for Dose

A planned dose range of 20 to 320 mg was selected to assess safety, tolerability, PK, and PD of LY3478045 following SAD and MAD in healthy subjects:

The planned starting dose in Part A (SAD) is 20 mg in both male and female subjects. The planned top dose in Part A (SAD) is a dose that is predicted to not exceed the mean exposure **CCI** (it is currently anticipated that this dose is 320 mg; however, the exact dose will be determined once PK data are analyzed from the previous cohorts in Part A).

The human PK in healthy subjects was projected with physiologically based pharmacokinetic (PBPK) modeling using data from in vitro studies in human systems. **CCI**

The predicted efficacious dose is 100 to 200 mg once daily based on maintaining plasma exposure over the total cell-based KHK half maximal inhibitory concentration for 24 hours. The PD measurement of serum fructose in Part A (SAD) will define the level of target engagement at each dose, which will further allow refinement of predicted efficacious dose.

The starting dose of **CCI**

[REDACTED]

The dose levels in MAD (Part B) will be selected based on available PK/PD data from Part A. The maximum dose in males in the MAD will be determined based on the PK analyses from previous cohorts to ensure that the predicted mean exposure AUC0-24 at the maximum dose in males does not **CCI**. This is 1/10th of the mean exposure level observed at 75 mg/kg in dogs, which is the lowest dose tested in dogs with no testicular findings. The maximum dose in females in the MAD will be determined based on the PK analyses from previous cohorts to ensure that the predicted mean exposure AUC0-24 at the maximum dose in females does not exceed **CCI**. This is 1/12th of NOAEL exposure at **CCI** dose in dogs.

Table GZKA.2.

CCI

CCI

CCI

6. Study Population

Eligibility of subjects for the study will be based on the results of screening medical history, physical examination, vital signs, clinical laboratory tests, and ECG.

The nature of any conditions present at the time of the physical examination and any preexisting conditions will be documented.

Screening may occur up to 28 days prior to day of clinical research unit (CRU) admission. Subjects who are not enrolled within 28 days of screening may be subjected to an additional medical assessment and/or clinical measurements to confirm their eligibility.

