7.1. Treatment Administered

LY3478045 or placebo will be administered orally with approximately 240 mL of room temperature water in the morning of each dosing day (Day 1 in SAD; Days 1 to 14 in MAD) in a sitting position. Subjects will not be allowed to lie supine for 2 hours after dosing, unless clinically indicated or for study procedures.

Table GZKA.3. Treatments Administered

Treatment Name	LY3478045	Placebo	Atorvastatin
Dosage Formulation	CC1	Capsules	Tablets
Dose strength		-	40 mg
Route of Administration	Oral	Oral	Oral

The investigator or designee is responsible for

- explaining the correct use of the investigational product(s) to the site personnel
- verifying that instructions are followed properly
- maintaining accurate records of investigational product dispensing and collection, and
- returning all unused medications to Lilly or its designee at the end of the study

Note: In some cases, sites may destroy the material if, during the investigative site selection, the evaluator has verified and documented that the site has appropriate facilities and written procedures to dispose off the clinical materials.

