9.3.1 Pharmacokinetic Statistical Methodology

All PK parameters will be summarized using descriptive statistics.

PK dose proportionality will be assessed separately for Parts A and B (on Day 14 for Part B). Log-transformed C_{max} , AUC_{T} (Part B only), and $AUC(0-\infty)$ of LY3478045 will be evaluated using a power model (where log-dose acts as an explanatory variable) to estimate ratios of dose-normalized geometric means and corresponding 90% confidence intervals (CIs). The estimated ratio of dose-normalized geometric means of PK parameters between the highest and lowest doses will be used to assess dose proportionality. A subinterval within the highest and lowest doses may also be considered for assessment of dose proportionality using the same approach. The dose proportionality analysis for Part B will only be conducted if there are at least 3 different LY3478045 dose levels available for analysis.

Examples of the SAS code that will be used are as follows:

```
proc mixed data=xxxx;
model log_pk = log_dose / alpha=0.1 cl solution outpred=resids ddfm=kr;
estimate 'xx mg' intercept 1 log_dose yy / alpha=0.1 cl; /*Log value of xx*/
estimate 'zz mg - xx mg' log_dose pp / alpha=0.1 cl; /*Difference in log
values of zz and xx*/
ods output solutionf=est;
ods output estimates=estims;
run;
```

In Part B, the PK parameters, AUC_{T} , $AUC(0-\infty)$, and C_{max} , will be log-transformed prior to analysis. A linear mixed effects model will be fitted to the data. The model will include Subject as a random effect, and Day as a fixed effect. For each PK parameter, the difference in least-square treatment means (Day 14 – Day 1) along with the 90% CIs will be back-transformed to produce the ratio of geometric means and the CIs comparing Day 14 to Day 1.

Example of SAS code as follows:

```
proc mixed data=xxxx;
by treatment;
class day subject;
model log_pk = day /residual ddfm=kr;
random subject;
lsmeans day / cl pdiff alpha=0.1;
ods output lsmeans=lsm diffs=estims;
run;
```

To assess the effect that LY3478045 has on the primary **CCI** PK parameters, $AUC(0-\infty)$ and C_{max} , a linear fixed effect model on the parameters will be used. The response of the model will be the logged ratio of observations on Day 7 to Day-2. The model will include Treatment and the log of the baseline (Day -2) observation as fixed effects. For the Day 7 observations in Cohorts 2 and 4, the difference in least-square treatment means ([LY3478045 + **CCI**] –

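### In Part B Cohorts 2 and 4, the 48 h sample of the Day -2 atorvastatin reference profile falls about 4 h after the first LY3478045 dose, so the LY-arm reference AUC(0-∞) is not fully LY-free

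*Protocol*

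**What the plan says.** The schedule for Cohorts 2 and 4 (Protocol Section 2.3) fixes the two probe doses: "Atorvastatin will be administered 4 hours after LY3478045 administration on Day 7 or 4 hours after breakfast on Day -2". Footnote d of that schedule sets the clock for the reference day: "Time of breakfast represents 0 min on study Day -2". The comment on the probe row ties its samples to the atorvastatin dose ("Sampling times are relative to the time of" atorvastatin administration; the phrase is split across rows). As extracted, the times for the reference period read "P, 0.5, 1, 2, 3, 4, 6, 20, 32 h", with 8 and 12 h wrapped onto a later line and 48 h in the next cell.

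Protocol Section 7.1 has LY3478045 or placebo given "in the morning of each dosing day (Day 1 in SAD; Days 1 to 14 in MAD").

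SAP Section 9.3.1 names AUC(0-∞) and Cmax as the primary probe parameters. "The response of the model will be the logged ratio of observations on Day 7 to Day-2", and the log of the Day -2 value is also a covariate. SAP Section 9.3 bases the extrapolated area on the predicted last concentration and the terminal slope.

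**The concern.** The Day -2 profile is meant to show atorvastatin without LY3478045. Its last scheduled point is drawn after LY3478045 has been given. Where that point is used, it enters the final trapezoid, the terminal slope and the predicted last concentration, so it can affect AUC(0-∞) in three ways.

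Only subjects on LY3478045 are affected. Placebo subjects' reference profiles stay clean, so the comparison with placebo does not cancel the error. If LY3478045 slows atorvastatin clearance, the LY-arm denominator is too large and the estimated interaction is too small. Part B is described as evaluating the potential for a drug-drug interaction, and an error towards no interaction is the less safe direction.

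**Working it through.** **1. Calendar.** The timing depends on whether there is a Day 0. The synopsis says "The planned duration for each subject is approximately 43 days in Part A and 57 to 59 days in Part B of the study", and Protocol Section 6 says "Screening may occur up to 28 days prior to day of clinical research unit (CRU) admission".

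| | No Day 0 | With a Day 0 | Stated |
|---|---|---|---|
| Part A | 28 + 1 + 14 = 43 | 44 | 43 |
| Part B, Cohorts 1 and 3 | 28 + 1 + 28 = 57 | 58 | 57 |
| Part B, Cohorts 2 and 4 | 28 + 3 + 28 = 59 | 60 | 59 |

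Only the calendar without a Day 0 reproduces the stated durations.

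**2. Sampling times.** Joining the wrapped cells gives predose, 0.5, 1, 2, 3, 4, 6, 8, 12, 20, 32 and 48 h. That is 12 times × 2 periods = 24 samples, and 24 × 2 mL = 48 mL. Appendix 5 has a row for Cohorts 2 and 4 with exactly 24 samples and 48 mL (label blacked out), and Section 9.5 gives 2 mL per atorvastatin sample.

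**3. Timeline, in hours from Day -2 breakfast.** Atorvastatin is at 4. The first LY3478045 dose is at 48, if the Day 1 dose has the same clock time as Day -2 breakfast.

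- 20 h sample: 4 + 20 - 48 = -24 h relative to LY3478045
- 32 h sample: 4 + 32 - 48 = -12 h
- 48 h sample: 4 + 48 - 48 = +4 h

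If the Day 1 meal (20 min after the dose) is aligned with Day -2 breakfast instead, the last figure is +4.3 h. Only the 48 h point is affected.

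**4. How far can 4 h of LY3478045 raise the 48 h value?** Assume LY3478045 acts on clearance, at once, from 44 h after atorvastatin. With terminal half-life t½, the 48 h value rises by f = 2^(2/t½) if clearance is halved, and by f = 2^(4/t½) if it is fully blocked.

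**5. Effect on AUC(0-∞).** Fit the log concentrations at 20, 32 and 48 h. The mean time is 33.33 h and the sum of squared deviations is 394.67. Multiplying the 48 h value by f has these effects:

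- the terminal rate λ falls by (14.67/394.67) × ln f = 0.0372 × ln f;
- the predicted last concentration is multiplied by f^0.878, since 1/3 + 14.67²/394.67 = 0.878;
- the 32 to 48 h log-trapezoid area grows.

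Example: t½ = 8 h, full block, true 48 h value set to 1.

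- λ = 0.0866, f = 1.414, refitted λ = 0.0738, predicted last value = 1.356.
- Tail: 1/0.0866 = 11.54 becomes 1.356/0.0738 = 18.38, a gain of 6.84.
- 32 to 48 h: 16 × (4 - 1)/ln 4 = 34.62 becomes 16 × (4 - 1.414)/ln(4/1.414) = 39.79, a gain of 5.17.
- If the true tail is 5% of the total, the total is 11.54/0.05 = 230.8, and the error is (6.84 + 5.17)/230.8 = 5.2%. With a 2% tail it is 2.1%.

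| t½ | f, halved | Error (2% to 5% tail) | f, blocked | Error (2% to 5% tail) |
|---|---|---|---|---|
| 8 h | 1.19 | 0.9% to 2.4% | 1.41 | 2.1% to 5.2% |
| 14 h | 1.10 | 0.5% to 1.2% | 1.22 | 1.0% to 2.5% |

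Half-life, tail share and strength of effect are assumptions; the documents give none of them. A one-compartment simulation over a wider range of half-lives, 7 to 30 h, gave about 0.5% to 10% for AUC(0-∞). For AUC(0-tlast) it gave 0.3% to 1.2%.

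**6. Passage through the model.** If the log(Day -2) covariate has coefficient b, modelling log(Day 7/Day -2) is the same as modelling log(Day 7) with baseline slope 1 + b. An overstatement d (log scale) of the LY-arm baseline moves the treatment effect by -(1 + b) × d. At b = 0 the shift is -d; for b between -1 and 0 it is smaller. As an illustration at b = 0, suppose halved clearance gives a true ratio of 2.00. The estimate would then be between 2.00/1.024 = 1.95 and 2.00/1.005 = 1.99.

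**The case against.** The best counter-argument is that the error is too small to matter. The interaction is an exploratory objective (SAP Section 4.3), and each of these cohorts has 6 LY3478045 and 2 placebo subjects. Take placebo pooled to 4, three treatment groups plus the covariate (16 - 4 = 12 degrees of freedom), and an assumed SD of the log ratio of 0.15 to 0.30. The 90% half-width is then 1.782 × SD × √(1/6 + 1/4) = 0.173 to 0.345, so the upper limit lies 19% to 41% above the estimate. A 0.5% to 5% shift is well inside that. This stands, and it is why the point is a refinement.

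There are also partial safeguards. A 48 h value below quantification would be set to missing. Terminal points are chosen by eye for each subject. A questionable value is reported with and without it. Time points are approximate and adjustable by the investigator. These make the error conditional, but none requires the sample before the dose or removes it from AUC(0-∞). The fixed-time AUC in SAP Section 9.3 is optional, for the case where AUC(0-∞) cannot be determined for all subjects. A rise of 10% to 20% at one late point could easily pass unnoticed.

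A reader might also infer that the bias is doubled because the Day -2 value is both denominator and covariate. It is not: step 6 shows that a negative covariate coefficient damps it.

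**Conclusion.** The timing follows from the protocol's own figures: the last reference sample is scheduled about 4 h after the first LY3478045 dose. The resulting error in the LY-arm reference AUC(0-∞) is about 0.5% to 5%, towards no interaction. This holds only if the 48 h value is quantifiable and used and LY3478045 slows atorvastatin clearance, under the half-life, tail and terminal-point assumptions above. It is zero if LY3478045 has no effect on atorvastatin. Cmax is unaffected if it occurs before 44 h.

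A reader might infer a much larger bias, for example by supposing that the 48 h concentration doubles. The same refit would then give about 5% to 16%. The documents do not support that case. With LY3478045 on board for only 4 h, even full and immediate block of clearance caps the rise at 1.22- to 1.41-fold for half-lives of 14 to 8 h. A doubling would need an abrupt rise that clearance does not explain. Nor do the documents support calling the interaction assessment invalid: this is a small, one-sided and avoidable error in one of its two primary parameters.

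**What to change.** Before sampling: move the last reference sample to just before the Day 1 dose, about 44 h after atorvastatin. Use the matching 44 h time after the Day 7 atorvastatin dose, and state the predose requirement in the Section 2.3 comment. This moves one sample by about 4 h in each period and adds none. The terminal phase is slightly shorter: a 2% to 5% tail at 48 h becomes 2% × 2^(4/14) = 2.4% to 5% × 2^(4/8) = 7.1% at 44 h.

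If samples are already taken: specify in SAP Section 9.3.1 that the 48 h point is excluded in both periods, or that AUC(0-32 h) is compared, at least as a sensitivity analysis. Dropping 48 h raises the extrapolated share to between 2% × 2^(16/14) = 4.4% and 5% × 2^(16/8) = 20%. The top of that range sits at the SAP's flagging limit, so AUC(0-32 h), which needs no extrapolation, is a useful companion.

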3.1. Study Rationale

Lilly is developing LY3478045, a ketohexokinase (KHK) inhibitor, that helps in attenuation of fructose metabolism thus, anticipated to result in

- reduction of liver fat, inflammation, and fibrosis
- improvement in glycemic control
- insulin sensitization, and
- reduction in body weight, free fatty acids, and triglycerides.

Study J2M-MC-GZKA (GZKA) is a first-in-human study, which aims to assess the safety, tolerability, pharmacokinetics (PK), and pharmacodynamics (PD) of single and multiple oral doses of LY3478045 in healthy subjects. The PK, PD, safety, and tolerability data from this study in healthy subjects will assist in identifying an appropriate dose range for subsequent clinical studies in patients with nonalcoholic fatty liver disease (NAFLD) and nonalcoholic steatohepatitis (NASH).

3.2. Background

3.2.1. Nonalcoholic Steatohepatitis

Sugar consumption has significantly increased over the several decades; the per capita consumption of dietary fructose has increased 100-fold and fructose now accounts for approximately 10% of calorie intake in the United States (Bray et al. 2004; Tappy and Mittendorfer 2012). Furthermore, the polyol pathway, which converts glucose into fructose, is active in tissues including the liver, heart, and kidney. Activity of the polyol pathway is increased in metabolic disease conditions resulting in higher levels of endogenous fructose generated from glucose (Lanaspa et al. 2013; Andres-Hernando et al. 2019).

While modest amount of fructose found in fruits and vegetables is not of concern, the increased intake of sucrose (50% glucose/50% fructose) and high fructose corn syrup (55% to 90% fructose) is considered to be a cause for metabolic disease and complications including NAFLD/NASH.

Nonalcoholic steatohepatitis is the progressive stage of NAFLD, characterized histologically by the presence of steatosis, lobular inflammation, and hepatocyte injury (ballooning), with or without fibrosis (Chalasani et al. 2018).

Nonalcoholic steatohepatitis is currently the third most common cause of hepatocellular carcinoma (Chalasani et al. 2018) and NASH is expected to become the leading cause of liver transplantation in the future (Charlton et al. 2011).

Patients with NASH with fibrosis are at a higher risk of adverse outcomes, including liver cirrhosis, liver-related mortality, and cardiovascular (CV) mortality (Angulo et al. 2015). There is a high unmet medical need for safe and effective pharmacological treatments for NASH, as no approved therapies are currently available (Younossi et al. 2018).

3.2.2. *Ketohexokinase*

Ketohexokinase (also known as fructokinase) is the enzyme responsible for the first step in fructose metabolism (phosphorylation of fructose to fructose 1-phosphate).

As fructose (exogenous or endogenous), per se, is biologically inactive, metabolism by KHK is required to elicit negative metabolic phenotype(s) associated with fructose intake, including NAFLD/NASH and insulin resistance. Excessive fructose flux through KHK causes pro-lipogenic and inflammatory profiles in the liver where KHK is abundantly expressed and is the primary site of fructose metabolism (Hannou et al. 2018).

Various epidemiological and human intervention studies revealed the association of fructose consumption with insulin resistance (Basciano et al. 2005), NAFLD/NASH (Vos and McClain 2009; Weber et al. 2018), CV disease (Fung et al. 2009; de Koning et al. 2012), and accompanying mortality (Collin et al. 2019). Conversely, significant metabolic benefits from isocaloric fructose restriction in human intervention trials that may be anticipated by reducing fructose metabolism (via KHK inhibition) include

- reduced liver steatosis
- suppressed hepatic de novo lipogenesis
- decreased inflammation, and
- improved insulin sensitivity.

As KHK acts as the gatekeeper to fructose metabolism and associated adverse phenotypes, reducing fructose metabolism via KHK inhibition is anticipated to mimic the isocaloric fructose restriction profiles.

Ketohexokinase as a Therapeutic Target

KHK inhibition (via mouse knockout, siRNA, small molecule) in nonclinical animal models support efficacy in NAFLD/NASH (Ishimoto et al. 2012, 2013; Lanaspa et al. 2013, 2018; Softic et al. 2017).

[figure not shown]
Human genetic validation of KHK as a therapeutic target exists based on loss of function mutations which results in essential fructosuria, an autosomal recessive disorder (Laron 1961; Froesch 1969; Bonthron et al. 1994). Individuals with this benign condition have inactive isoforms of KHK, limiting the liver's ability to metabolize and clear fructose upon fructose ingestion, increased fructose excursion into the serum, and ultimately excretion of fructose into urine. Due to the low prevalence of condition (approximately 1/100,000) and/or its benign nature, individuals with essential fructosuria have not been characterized well enough to define potential metabolic phenotype improvements. However, characterization of these individuals supports the notion that a KHK inhibitor is anticipated to eliminate excess carbohydrates without a mechanism-based safety issue.

A clinical trial (Calle et al. 2019) in patients with NAFLD treated for 6 weeks with a KHK inhibitor revealed

- statistically greater reduction from baseline in the whole liver fat

- dose-dependent decrease in fasting insulin and insulin resistance
- dose-dependent percent changes in high-sensitivity C-reactive protein (reduction) and adiponectin (increase), and
- six weeks of KHK inhibition was demonstrated to be safe and well tolerated.

